#### **5. Study Intervention/Design**

Patients will be randomized to either:

- (1) In person LCS intervention** - With *Opioid Risk Education*, patients will receive opioid education after completing the validated Opioid Risk Tool (ORT), a detailed substance abuse survey and mental health screening, and Naloxone education. *Therapeutic Intervention* will include the Community Resiliency Model (CRM). *Clinical Pain Coordination* will include directed referrals for complex needs, including mental health and substance use disorders, as needed. In addition to above mentioned 3 intervention components, all patients in the LCS intervention arm will also receive the current standard-of-care. The Community Resiliency Model (CRM) is a noncognitive variant of mindfulness, emphasizing attunement to interoceptive and exteroceptive signaling cues for regulation of autonomic responses to stress (Grabbe, Higgins, Baird, Craven & San Fratello, 2020). CRM was derived from somatic psychotherapy and self-stabilization interventions using body sensation awareness. Body sensation awareness is called introspection and is a key component of mindfulness. Awareness of internal body sensation occurs in the insular cortex and adjacent brain structures, which serve as cerebral centers regulating emotional regulation, empathy, and social interaction (Simmons et al., 2013). Implementing these techniques may preventatively attenuate the immediate impact of stressors. For example, the CRM model has been implemented across several settings and populations and has been associated with improved well-being, resiliency, and physical symptoms (Grabbe et al., 2020; Grabbe et al., 2021; Habimana et al., 2021). CRM skills are introduced over a sixty-to-ninety-minute session, allowing for a brief introduction and application of skills by participants.

- (2) **Virtual LCS intervention** - With *Opioid Risk Education*, patients will receive opioid education after completing the validated Opioid Risk Tool (ORT), a detailed substance abuse survey and mental health screening, and Naloxone education. *Therapeutic Intervention* will include the Community Resiliency Model CRM).. *Clinical Pain Coordination* will include directed referrals for complex needs, including mental health and substance use disorders, as needed. In addition to above mentioned 3 intervention components, all patients in the LCS intervention arm will also receive the current standard-of-care.

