- (3) **No LCS intervention** - Patients will receive the current standard-of-care for pain management in the aftermath of surgery, which includes: a standardized prescription protocol, hospital-system approved discharge instructions which provide written instruction on how to taper opioid use, links to written/online resources for opioid misuse, overdose prevention, and State-approved disposal options.

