- Opioid utilization: Inpatient and operating room opioid utilization will be extracted from the electronic health record (EHR) by study staff upon participants' discharge from the hospital. Opioid medication dosage will be transformed to a total universal measure known as morphine milligram equivalent (MME). MME will be averaged over the length-of-stay (LOS) for a daily dosage, known as MME/day. Additionally, the study team will review participants' EHR at each study time point up to 3-months to determine MME throughout postoperative recovery and rehabilitation. Medication Electronic Monitoring (MEMS) devices will be used to assess medication utilization and adherence rates. They are Bluetooth enabled caps that fit on standard medicine bottles and record participants' medication utilization. Participants will be dispensed their opioid medication by the pharmacy in the MEMS equipped containers and informed to return their bottle at their next follow up visit.
- Pain numerical rating scale (NRS): The NRS requires respondents to rate the intensity of their pain on a defined scale from 0, "no pain", to 10, "the worst pain imaginable". The NRS is a commonly used pain assessment tool in both clinical practice and

research. (Farrar et al., 2010) However, the NRS is a single static measure of pain and does not capture the biopsychosocial presentations of pain including physical functioning. As such a battery of objective (e.g. actigraphy) and patient-reported outcomes are needed to best ascertain patient participants' pain experiences. Inpatient NRS, which is recorded by the clinical care team throughout each day, will be extracted from the electronic health record (EHR) by study staff upon participants' discharge from the hospital.

- Mindful Attention Awareness Scale: The MAAS is a validated 15-item scale designed to assess a core characteristic of dispositional mindfulness, namely, open or receptive awareness of and attention to what is taking place in the present.

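### Dividing inpatient MME by length of stay can reverse the sign of a real fall in opioid use, and post-discharge MME is tied only to the health record, which does not observe tablets taken at home

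*Combined protocol and SAP*

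**What the plan says.** Hypothesis 1.2 (Section 2) predicts lower opioid use in the intervention arms, both in hospital and after discharge. Section 1 lists opioid use among the secondary objectives.

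For the hospital stay, Section 6 (opioid utilization item) says "Inpatient and operating room opioid utilization will be extracted from the electronic health record (EHR"), converts the doses to MME, and continues: "MME will be averaged over the length-of-stay (LOS) for a daily dosage, known as MME/day". No other inpatient score is named. LOS has no unit, and there is no rule for same-day discharge.

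After discharge there are two sources. The first is record review: "the study team will review participants' EHR at each study time point up to 3-months to determine MME throughout postoperative recovery and rehabilitation". The second is the monitored cap on the dispensed bottle: "Medication Electronic Monitoring (MEMS) devices will be used to assess medication utilization and adherence rates". The caps are said to "record participants' medication utilization", and the bottle goes back at the next follow-up visit. Section 4 likewise names records and remote monitoring together as the sources for opioid consumption. Nothing says how cap data become MME, which source is the outcome, or what happens when the two disagree. Section 19 names no opioid variable.

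Section 5 describes control care as including "a standardized prescription protocol, hospital-system approved discharge instructions", and says of the intervention that "all patients in the LCS intervention arm will also receive the current standard-of-care".

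**The concern.** Section 6 places randomisation and the LCS session before surgery, and Section 3 describes LCS work during the hospital stay. LOS is therefore a post-randomisation quantity that the intervention could change. Dividing by it mixes an effect on opioid use with an effect on time to discharge. The operating-room dose adds to the problem: it is given once at the start of the stay, so a shorter stay spreads it over fewer days. A patient who uses less opioid per ward day, and less in total, can then score higher on MME/day.

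After discharge, the only route to MME that Section 6 describes is the EHR. The record can show what was ordered or supplied, but it does not observe tablets taken at home. The caps are closer to consumption, but they have no route to MME, and by the return instruction they may stop at the first follow-up visit.

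At stake is the reading of Hypothesis 1.2 and of the opioid part of Aim 3. A true reduction could be reported as an increase in hospital, or diluted after discharge.

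**Working it through.** **Inputs.** From the documents: the scoring rule and bottle return (Section 6), follow-up at 2 weeks, 6 weeks and 3 months with a one-week window at the first visit (Section 6), and about 90 days in the study (Section 9). The documents give no MME or LOS values, so there is no planned figure to reproduce. Every dose and stay below is an assumption.

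**Condition for reversal.** Let r be the intervention/control ratio of total MME and l the ratio of LOS. For a pair of patients, the ratio of MME/day is r / l. When r < 1, this exceeds 1 exactly when l < r. With r = 0.8, l = 1, 0.9, 0.8, 0.67 and 0.5 give 0.80, 0.89, 1.00, 1.19 and 1.60.

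**Role of the operating-room dose.** With operating-room dose O, ward rate w per day and stay L days, total = O + wL and MME/day = w + O/L. The sign reverses when O(1/L_int - 1/L_con) exceeds w_con - w_int.

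**Illustration.** The ward rate is 25% lower with the LCS, and the stay is 1 day v 2 days in control.

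| O, control w | Total, LCS v control | Change | MME/day, LCS v control | Change |
|---|---|---|---|---|
| 40, 20 | 40+15 = 55 v 40+40 = 80 | 31% lower | 55 v 40 | 38% higher |
| 40, 30 | 40+22.5 = 62.5 v 40+60 = 100 | 38% lower | 62.5 v 50 | 25% higher |
| 60, 20 | 60+15 = 75 v 60+40 = 100 | 25% lower | 75 v 50 | 50% higher |
| 60, 30 | 60+22.5 = 82.5 v 60+60 = 120 | 31% lower | 82.5 v 60 | 38% higher |

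**Same first row with equal stays of 2 days.** LCS (40+30)/2 = 35 v control 40. The sign is kept.

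**Smaller differences in stay.** Ward rate 24 v 30 MME/day, control stay 2 days.
- O = 40, control (40+60)/2 = 50.0. LCS over 2 days: 88/2 = 44.0 (kept). Over 1.5 days: 76/1.5 = 50.7 (reversed). Over 1 day: 64.0 (reversed).
- O = 20, control 80/2 = 40.0. LCS over 1.5 days: 56/1.5 = 37.3 (kept). Over 1 day: 44.0 (reversed).
- O = 0: 24 v 30 at any stay (kept).

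**With variation between patients.** Simulation of 50 control and 100 intervention participants, 4,000 runs per setting. Total MME is lognormal with medians 60 v 48 (20% lower) and log SD 0.5. LOS is lognormal with control median 1.5 days and log SD 0.4, independent of total MME. Chance that the arm difference has the wrong sign:

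| LOS ratio | 1.0 | 0.9 | 0.8 | 0.7 | 0.6 |
|---|---|---|---|---|---|
| MME/day | 4% | 18% | 50% | 87% | 99% |
| Total MME | about 1% | about 1% | about 1% | about 1% | about 1% |

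**LOS unit.** 60 MME over 6, 8, 12, 23 and 36 hours is 60/(hours/24) = 240, 180, 120, 62.6 and 40 MME/day. If LOS is counted as 0 days, the score is undefined.

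**Cap coverage.** If the bottle is returned at the 2-week visit, the caps cover 14/90 = 16% of follow-up. If that visit is a week late (assuming the window runs after the due date), they cover 21/90 = 23%. Reissue of caps is not stated.

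**The case against.** The strongest reply is that reversal needs an arm difference in LOS, and the documents show none. If most procedures are same-day, there is also little stay to shorten. Both points stand, and a reader who inferred that the planned score is biased would go too far. But short stays do not rescue the measure. At 60 MME, leaving after 6 hours instead of 8 moves the score from 180 to 240/day, and the missing unit and same-day rule matter even with equal stays. Whether same-day discharge occurs is not stated; the injuries listed in Section 10 do not exclude it.

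It can also be said that Section 6 forms a total MME before averaging, so total MME is not ruled out as an outcome. That is true, but MME/day is the only inpatient score named.

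A reader might infer that post-discharge use is scored from EHR prescriptions alone, and so not measured as consumption at all. The documents do not support this. Sections 4 and 6 both add remote monitoring, and Section 6 speaks of EHR review to obtain MME without mentioning prescriptions. Nor do they support the inference that supply is identical across arms. A standardised protocol is not a fixed quantity, the discharge dose is abstracted for each participant, and later prescribing can differ. The most that follows is that supplied MME may separate the arms poorly.

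Finally, an obvious remedy has its own flaw. Dispensed minus returned tablets counts discarded tablets as taken. The LCS teaches disposal (Section 6), whereas controls receive written disposal options (Section 5), so the error could differ by arm. An inpatient total cut at a fixed hour has another flaw: it truncates patients who leave before that hour.

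**Conclusion.** The point holds as a risk in the definition of a secondary outcome. MME/day gives the wrong sign for a fall in total MME whenever LOS falls by a larger proportion, and a dose given once in the operating room makes this possible even when ward use per day also falls. In the first illustration the reversal occurs at all four corners: total MME is 25-38% lower and MME/day 25-50% higher. That rests on the assumed doses and on a halved stay. At equal LOS, or with no operating-room dose, the sign is kept in the cases worked. The dependence on the LOS unit needs no difference between arms.

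After discharge the gap is narrower. Consumption data are planned, but MME is linked only to the EHR, the caps have no stated conversion to MME, and they may cover only about 14 of 90 days. The definitions should be changed; the finding does not undermine the trial as a whole.

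**What to change.** In Section 6, for Hypothesis 1.2:

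- Replace MME/day with total MME from surgery over a window common to all participants, for example to the 2-week visit. Add MME administered in hospital to post-discharge use, so that early discharge does not truncate the total.
- Report operating-room MME separately. Keep MME/day as descriptive only, with LOS in hours.
- For post-discharge use to the 2-week visit, make MEMS the consumption source and state how cap data become MME. Support it with a count of returned tablets and a survey item on tablets taken and tablets discarded, asked remotely when the visit is by video. Say what applies when the sources disagree.
- Label EHR-derived MME after bottle return as opioid prescribed or supplied, not consumed.

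The cost is a definition change, a brief count at a return that is already planned, and one or two survey items. The in-hospital part uses records already being extracted, so it can also be applied to participants already enrolled. The tablet count and survey items cannot be recovered for those past the 2-week visit, so for them the post-discharge part would rest on cap data alone.

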## 2. Objectives

**Protocol Title:** Implementing and Evaluating the Effect of Personalized Pain Coaches After Orthopaedic Surgery for Patients with Sports Medicine Injuries to Improve Postoperative Outcomes

---

The *objective* of this randomized controlled trial is to examine how the integration of a trained Life Care Specialist improves postoperative recovery related to patient-reported pain outcomes, opioid utilization, and objective functional outcomes following orthopaedic injury.

**Aim 1:** Examine differences in post-surgical patient-reported pain related outcomes and opioid utilization between participants in the intervention arms compared to those in the control arm.

*Hypothesis 1.1:* Those randomized to the intervention arms will report improved average patient-reported pain related outcomes compared to participants in the control, standard of care, arm.

*Hypothesis 1.2:* Participants in the intervention arms will have decreased utilization of opioid pain medications both in the inpatient and outpatient setting.

**Aim 2:** Compare postoperative functional outcomes among intervention and control groups during their hospitalization and postoperatively.

*Hypothesis 2:* Objective functional outcomes captured from actigraphy devices will indicate improved physical functioning among those in the intervention arms compared to participants in the control arm.

**Aim 3:** Evaluate patient-reported pain related outcomes and opioid utilization between participants randomized to the in-person intervention and the telehealth delivered intervention arms.

*Hypothesis 3:* Improvements in patient-reported outcomes and opioid utilization will be similar across study arm groups, thereby indicating the utility of delivering the intervention both in person or remotely to improve care outcomes.

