#### **10. Inclusion and Exclusion Criteria**

We will recruit 150 participants from the orthopaedic sports medicine service at Grady and Emory Healthcare for this study. Individuals between 15–45 years old, scheduled for orthopaedic surgery due to sports medicine injuries (e.g., anterior cruciate ligament tears, meniscus injury, rotator cuff injury, etc.), and those who are actively employed or full-time athletes prior to injury will be eligible. Individuals unable to provide consent, those undergoing revision procedures, individuals without access to an internet connected device, and individuals who are unemployed or retired at time of injury will be ineligible. No one will be excluded from participation based on gender, race, or ethnicity. Individuals who are incarcerated or pregnant will not be eligible. Individuals unable to consent and those unable to communicate in English will be excluded since all surveys are validated in English.

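### The operating-room opioid dose is counted in the inpatient MME/day score, so short stays inflate the score and any coaching effect on inpatient use is diluted

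*Combined protocol and SAP*

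**What the plan says.** The opioid utilization item in section 6 (Procedures Involved) opens: "Inpatient and operating room opioid utilization will be extracted from the electronic health record (EHR) by study staff". Doses are converted to a total in morphine milligram equivalents, and then "MME will be averaged over the length-of-stay (LOS) for a daily dosage, known as MME/day". The operating-room dose is not separated from the ward dose. The unit of length of stay is not defined, and same-day discharge is not covered. Section 19 (Data Analysis) names a mixed model but no adjustment for length of stay.

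The score serves Hypothesis 1.2 in section 2: "Participants in the intervention arms will have decreased utilization of opioid pain medications both in the inpatient and outpatient setting". Section 10 enrols patients "scheduled for orthopaedic surgery due to sports medicine injuries (e.g., anterior cruciate ligament tears, meniscus injury, rotator cuff injury, etc". Section 6 also provides two opioid measures that are not divided by inpatient stay: MEMS bottle caps, and a record review in which "the study team will review participants' EHR at each study time point up to 3-months to determine MME throughout postoperative recovery and rehabilitation". Section 1 lists opioid utilization as a secondary objective, although section 2 also places it in Aims 1 and 3.

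**The concern.** The operating-room dose is a one-off amount given during surgery. A coaching session held beforehand can hardly change it. Once that dose is divided by length of stay, its weight in the score depends on how long the patient stays: large for a short stay, small for a long one. The eligible procedures make short stays plausible, although the documents do not say how long patients stay.

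Two harms follow. With similar stays in all arms, a real reduction in ward use appears as a much smaller relative change in a noisier score. With shorter stays in the LCS arms, the score is pushed up in those arms. MME/day is the only inpatient opioid summary the protocol specifies, so the inpatient half of Hypothesis 1.2 rests on it.

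**Working it through.** **Inputs.** The numerator and denominator come from section 6, and the total of 150 from section 10. The documents give no allocation ratio, so I assume 1:1:1 (100 LCS, 50 control). They also give no MME values, stays, standard deviations, alpha or power. There is therefore no plan figure to reproduce, and every dose and stay below is an assumption.

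**1. Form of the score.** With operating-room dose F, ward rate r per day and stay L in days:

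score = (F + rL)/L = F/L + r

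LCS minus control = (r_T − r_C) + F(1/L_T − 1/L_C)

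**2. Inflation by short stays.** Take F = 25 and r = 30. A stay of 0.33 day scores 25/0.33 + 30 = 106 MME/day. A stay of 2 days scores 25/2 + 30 = 42.5. The two patients have the same operating-room dose and the same ward rate.

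**3. Dilution with equal stays.** Assume stays of 0.4, 1.1 and 2.1 days in 60%, 30% and 10% of patients in every arm. Mean 1/L = 0.6/0.4 + 0.3/1.1 + 0.1/2.1 = 1.820. With F = 25 the control mean is 25 × 1.820 + 30 = 75.5. A true 30% cut in ward rate (30 to 21) gives 66.5, so it shows as 9/75.5 = 12%.

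**4. Power with equal stays.** Simulation with 4,000 runs, 100 versus 50 patients, the same mix of stays, lognormal F (log SD 0.5) and r (log SD 0.6), a true 30% cut, and a Welch t-test on logs at two-sided 0.05:

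| Mean F (MME) | MME/day with operating-room dose | Ward MME divided by stay |
|---|---|---|
| 15 | about 54% | about 92% |
| 25 | about 33% | about 92% |
| 40 | about 20% | about 92% |

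The right-hand column still divides by length of stay. The gain comes from removing the operating-room dose.

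**5. Shorter LCS stays, fractional days.** Change the LCS mix to 70%, 25% and 5%. Mean 1/L = 0.7/0.4 + 0.25/1.1 + 0.05/2.1 = 2.001. With F = 25:
- a true 10% cut gives 25 × 2.001 + 27 = 77.0 against 75.5, which is 2% higher;
- a true 20% cut gives 74.0, which is 2% lower;
- power for a true 30% cut is about 11%.

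The benefit vanishes at L_T = F/(F/L_C + r_C − r_T). For a 20% cut (6 MME/day) from a 1-day control stay, F = 20 gives 20/26 = 0.77 day (23% shorter) and F = 80 gives 80/86 = 0.93 day (7% shorter).

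**6. Whole-day stays.** Round up with a minimum of 1, so that 0.4, 1.1 and 2.1 become 1, 2 and 3 days. With F = 25 and a true 10% cut:
- control: 0.6 × 37 + 0.3 × 58/2 + 0.1 × 88/3 = 33.8;
- LCS, shorter stays: 0.7 × 35.8 + 0.25 × 54.7/2 + 0.05 × 81.7/3 = 33.3.

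The direction is right, but the fall is under 2%. Power for a true 30% cut with equal stays is about 47%. If midnights are counted instead, a same-day stay has length 0 and no score.

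**7. Total inpatient MME as an alternative.** Mean stay is 0.78 day in control and 0.66 day in the shorter LCS mix. With r = 30 in both arms, totals are 25 + 23.4 = 48.4 and 25 + 19.8 = 44.8. That is a 7.4% fall with no change in the rate of use.

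**The case against.** The strongest reply is that dividing by time is the ordinary correction for unequal observation, and this stands. Step 4 shows that length of stay as a denominator does no harm once the operating-room dose is out and the ward rate is roughly constant. A reader might infer that stay must never be a denominator; the calculations do not support that. Nor does the score simply rank patients the wrong way. The two patients in step 2 have the same ward rate, and one is merely observed for less time.

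A reader might also infer that the planned score will hide or reverse a true benefit. In expectation, reversal needs shorter LCS stays. No section states this, though coaching precedes surgery, so an effect on stay cannot be excluded. It also depends on how stay is counted: the reversal in step 5 uses fractional days, and whole days with a minimum of 1 did not reverse the same example. With equal stays the expected difference keeps its sign and its absolute size.

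Two further points stand. Section 6 never writes the formula, so including the operating-room dose is the natural reading rather than an explicit one. And only the inpatient part of an objective listed as secondary is affected. What the reply does not answer is the dilution, which needs no difference in stay.

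**Conclusion.** The concern holds as a flaw in the definition of one secondary measure. As naturally read, section 6 mixes a dose that coaching can hardly change into the inpatient score, with a weight that grows as the stay shortens. Under the assumed values, power for a 30% reduction in ward use with equal fractional-day stays falls from about 92% to between 20% and 54%. The direction follows from the algebra; the size rests on assumed doses, stays, spreads and 1:1:1 allocation, and the 92% also assumes that ward use is recorded without error. Bias against the LCS, up to loss or reversal of the benefit, is conditional on earlier LCS discharge and on fractional-day counting. The documents establish neither. The patient-reported pain outcomes, the 3-month record MME and the MEMS data are not touched. The definition should be corrected before analysis, but the flaw does not put the trial's main objective in doubt.

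**What to change.** Amend the opioid utilization item in section 6 and carry the change into section 19:

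- Report operating-room MME separately and leave it out of the comparison of arms.
- Compare postoperative MME per unit of time observed from leaving the operating room, or over a fixed postoperative window that every patient completes in hospital. The fixed window is safer if dosing is concentrated soon after surgery, because a rate averaged over the stay would then again depend on its length.
- Abstract dates and times so that stay is in hours and same-day patients are kept in.
- Report length of stay as its own outcome.
- Do not substitute total inpatient MME alone, for the reason in step 7.

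The cost is a wording change and time-stamped abstraction from the health record that staff already review. Home-use data are needed only if the chosen window runs past discharge; the MEMS caps could contribute to these, with whatever gaps they have.
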